1 PROTOCOL SUMMARY

1.1 SYNOPSIS

Title:

Utilizing Changes in Human Brain Connectivity to Establish a Dose-Response Relationship Involved in the Therapeutic Actions of Prefrontal Brain Stimulation on Depression Symptoms

Study Description:

This double-blind, randomized, sham-controlled mechanistic study aims to establish a resting-state functional connectivity (RS FC) dose-response curve associated with the therapeutic actions of our accelerated intermittent theta-burst stimulation (aiTBS) neuromodulation approach in outpatients diagnosed with Major Depressive Disorder (MDD) as defined by DSM-5 criteria. We will accomplish this by applying the aiTBS protocol (10 daily interventions of aiTBS to a customized target within the left dorsolateral prefrontal cortex identified with fMRI for five consecutive days) and measuring RS FC between the subgenual anterior cingulate cortex (sgACC) and the default mode network (DMN) after each day of intervention. We then will determine the relationship between changes in the RS FC and both changes in clinical symptoms of depression (24 hour version of the Montgomery-Asberg Depression Rating Scale-Self Report [MADRS-S]) and acute mood state (Immediate Mood Scaler [IMS-12]). Our mechanistic hypothesis is that the nature of the improvement in mood will be linear, related to session number (accumulated pulse dose), and correlated with degree of change in RS FC between the sgACC and DMN.

Objectives:

Primary Objective:

The primary objective of this investigation is to establish a resting state functional connectivity (RS FC) dose-response curve of active versus sham aiTBS.

Secondary Objectives:

(a) To determine the relationship between active versus sham aiTBS-induced clinical improvement (as measured by reduction of the MADRS-S) and changes in RS FC between the sgACC and DMN.

(b) To determine the relationship between acute mood state (as measured by the IMS-12) and changes in RS FC between the sgACC and DMN in those receiving active versus sham aiTBS.

Primary Endpoint:

Change in RS FC between the sgACC and DMN over 5-days of active aiTBS as compared to sham aiTBS.

Endpoints:

Secondary Endpoints:

(a) Relationship between clinical improvement (measured by the MADRS-S) and RS FC between the sgACC and DMN.

(b) Relationship between acute mood state (measured by the IMS-12) and RS FC between the sgACC and DMN.

Study Population:

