Our lab's accelerated intermittent theta-burst stimulation (aiTBS) protocol is a form of neuromodulation that induces remission in 90% of individuals with TRD within 1-5 days¹⁴⁹. This study addresses our current limitations of understanding the MOA of aiTBS's dramatic therapeutic¹⁴⁹ and network-level effects¹⁵⁰. This study will provide an opportunity to iteratively assess changes in RS FC after each day of stimulation (i.e., every 18,000 pulses - which is equivalent to an entire conventional 6-week course of iTBS⁸⁰) and thereby establish a dose-response relationship between stimulation and change in RS FC at our target (sgACC-DMN)⁸⁶. This study is the only way to accomplish this because if one assumes that the rate of decrease is linear, recent data demonstrate a 12 point per day decrease in the HDRS-17⁸⁶, and given that the high end of the scale is a 52, it would take 5 days to reduce the score from 52 to remission range. To apply 7.5 months (5X dose of traditional) of once per day of rTMS would be infeasible from a clinical study standpoint. Otherwise, there would be a high expected regression to the mean of a sample receiving 5 times the conventional 6-week course (7.5 months long duration of therapy if given by conventional

means)¹⁵¹. We recently demonstrated a significant reduction in mean sgACC-DMN connectivity after aiTBS with significant reductions in fc between sgACC and 3 of 4 DMN nodes¹⁵⁰. Individual changes in fc magnitude showed that participants with the lowest magnitude reductions in fc between sgACC and midline DMN experienced the best clinical improvements. This makes sense in the context of the longitudinal fc changes induced by ECT where an early fc decrease significantly predicted a later increase in fc¹⁵². These findings may suggest that less or more sessions of aiTBS would result in differential fc/clinical outcomes and illustrate the need for this study to construct an fc-based dose-response curve.

Innovation:

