This study is **innovative** technologically in its approach to rapidly modulate the neural circuitry underlying depression and measure the functional connectivity changes resulting from that modulation using precision medicine. This efficacy and rapidity is achieved via several technological innovations over conventional rTMS: 1) The number of pulses given per day (18,000) is higher than any other known application, and this may address potential under dosing of rTMS in treatment of depression^{84,90}. 2) iTBS is more efficient than rTMS at a pulse ratio of 1:5 with 1 pulse of iTBS equivalent to 5 10Hz rTMS pulses and at a time ratio of 1:12.3 with every 1 min of iTBS being equivalent to 12.3 min of 10Hz rTMS⁸¹. 3) We space iTBS sessions at 60-min intervals, which may be optimal for producing long-term potentiation via iTBS as shown by studies of synaptic potentiation¹⁵³. Notably, theta-burst trains that are spaced by 60 min result in over twice the magnitude of potentiation as trains spaced by 30 min, and trains spaced by 60 min induce the same magnitude of synaptic potentiation as those spaced by 90 min¹⁵³. 4) We account for the significant variability in head anatomy¹⁵⁴. 5) We employ an automated personalized targeting approach based a hierarchical clustering algorithm to identify functional subregions of the L-DLPFC & sgACC. A separate decision-making algorithm then evaluates the size, shape, and the functional connectivity relationships between each L-DLPFC subregion and each sgACC subregion in order to identify the optimal L-DLPFC target with an existing anti-correlation functional connectivity relationship with the sgACC. The advantages of aiTBS also include more rapid delivery of treatment, more rapid improvement in symptoms, and fewer needed visits; thus, likely enhancing retention and treatment completion. aiTBS provides a new opportunity to begin investigating the network alterations underlying MDD remission. Fc changes that occur with aiTBS may reflect generalized network-level changes associated with remission from depression. Given that we found that fc significantly decreases between several of these regions following aiTBS-induced remission from MDD, the magnitude of fc change often correlating with symptom improvement, and the pre-treatment connectivity between several regions to be predictive of the magnitude of this improvement, this study will allow for an opportunity to study the nature of the trajectory of the fc changes in relation to clinical changes^{5,86}.

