3 OBJECTIVES AND ENDPOINTS

OBJECTIVES	ENDPOINTS	JUSTIFICATION FOR ENDPOINTS
Primary		
To establish a resting state functional connectivity (RS FC) dose-response curve of active versus sham aiTBS.	Change in RS FC between the sgACC and DMN over 5-days of active aiTBS as compared to sham aiTBS. RS FC will be measured on the morning of each intervention day and the day following intervention.	We hypothesize that participants (n=50) receiving active aiTBS applied to DLPFC-sgACC will demonstrate a significant attenuation of RS FC between sgACC and DMN compared to sham (n=50) after each day of stimulation and these effects will accumulate linearly over the course of the 5 days of aiTBS. The central, consistent change in neurocircuitry observed in depression is hyperconnectivity between the SCC and DMN ⁴³ and our preliminary data involving RS FC changes from aiTBS demonstrates highly significant changes ¹⁹⁴ .
Secondary		

(a) To determine the relationship between active versus sham aiTBS-induced clinical improvement (as measured by reduction of the MADRS-S) and changes in RS FC between the sgACC and DMN.
 
(b) To determine the relationship between acute mood state (as measured by the IMS-12) and changes in RS FC between the sgACC and DMN in those receiving active versus sham aiTBS.
	
(a) Relationship between clinical improvement (measured by the MADRS-S) and RS FC between the sgACC and DMN.
 
MADRS-S will be collected at baseline, the end of each intervention day, the day following intervention, and 1-month after intervention. RS FC will be measured on the morning of each intervention day and the day following intervention.
 
(b) Relationship between acute mood state (measured by the IMS-12) and RS FC between the sgACC and DMN.
 
IMS-12 will be collected at baseline, on the morning of each intervention day, and the day following intervention. RS FC will
	Our mechanistic hypothesis is that active versus sham aiTBS-induced improvement in mood will be linear, related to session number (accumulated pulse dose), and will be associated with (accumulated) decrease in sgACC- DMN resting state functional connectivity, as compared to sham.

	be measured on the morning of each intervention day and the day following intervention.	
Exploratory		

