9.2 SAMPLE SIZE DETERMINATION

Sample size justification (power analysis):

Key Hypothesis of the study: A significant reduction in functional connectivity between sgACC and DMN. We hypothesize that the reduction in functional connectivity between the subgenual cingulate cortex and the default mode network from baseline to after intervention day 5 will be significantly greater for participants receiving active compared to sham aiTBS. Several past studies have found no significant changes in functional connectivity with sham rTMS targeted to DLPFC^{136,212}. Using preliminary data from our open-label study of aiTBS for treatment of severe depression, there was an effect size of 1-1.47 (depending on DMN node) for change in connectivity between sgACC and DMN¹⁵⁰. One potential approach for determining the power calculation would be that considering we will have 10 unique comparisons with each day's data be compared to every other day over 5 days, and that we will be comparing across 4 DMN nodes and 2 sgACC nodes, our target alpha needs to be $0.05/(10*4*2) = 0.000625$. Thus, for an effect size of 1, alpha of 0.000625, and a power of 0.80, and powering for an independent-measures t-test, 40 participants will be required for each arm. Regarding our secondary mechanistic endpoints, we have previously found a significant correlation between change in FC between sgACC and DMN in participants receiving open-lab aiTBS, Pearson $r = 0.51$. For a point biserial model, a two-tailed 2 test, and a power target of 0.80, 25 participants will be required for each group.

Our recruitment goals are based on our primary mechanistic endpoint. Considering a ~25% attrition rate (combined participants lost to followup and unusable or missing scans), **we plan to recruit 50 participants in each arm**, as this is larger than the 18 per arm that is required to power for a significant reduction in IMS-12, and large enough to provide sufficient power for our secondary mechanistic endpoints. Given that there are ~1,000 new depressed patients at Stanford per year, >75% are TMS-naïve, there are many more than 100 patients per year that meet inclusion criteria.

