9.4.3 ANALYSIS OF THE SECONDARY ENDPOINT(S)

Our secondary hypotheses are:

- (a) We hypothesize that there will be a significantly greater association between the change in depression symptoms (as measured by the MADRS-S) and the change in resting-state functional connectivity between the subgenual anterior cingulate cortex and the default mode network from baseline to after intervention day 5 for participants receiving active as compared to sham aiTBS.
- (b) We hypothesize that there will be a significantly greater association between acute mood state (as measured by the IMS-12) and the change in resting-state functional connectivity between the subgenual anterior cingulate cortex and the default mode network from baseline to after intervention day 5 for participants receiving active as compared to sham aiTBS.

We will use fMRI to measure resting-state FC between sgACC & DMN. Participants will be treated for 5 consecutive days with 10 sessions per day of active or sham aiTBS. Participants have a baseline MRI scan prior to each day of aiTBS intervention as well as the day following the completion of intervention. After standard preprocessing of fMRI data, we will calculate FC as the correlation of the activity pattern across time between the sgACC and DMN regions of interest. All correlation coefficients will then be transformed into Fisher's Z score for further analysis.

MADRS-S will be collected at baseline, the end of each intervention day, and the day following intervention. IMS-12 will be collected at baseline, on the morning of each intervention day, and the day following intervention.

Normality in change in both assessments and change in FC from baseline to post-intervention will be assessed via Shapiro-Wilk. Appropriate correlational analysis (Pearson or Spearman) will be used to quantify the association between change in FC and change in each assessment for each treatment group. Correlation coefficients will be compared statistically by performing Fisher's R-to-Z transformation and the difference between the two Z-scores will be tested for statistical significance using a two-tailed Z-test with an alpha level of 0.05 ($p < 0.05$). The null hypothesis, i.e. no difference in the association between change in FC and change in each assessment between groups, will be rejected if the Z-test has a p-value < 0.05 .

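### The secondary mood-connectivity test sets no direction, although section 3 predicts one and the individual-level pilot result in section 2.1 points the other way

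*Combined protocol and SAP*

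**What the plan says.** **Predicted direction.** Section 3, in the justification for the secondary endpoints, expects mood improvement to be linear and says that it "will be associated with (accumulated) decrease in sgACC- DMN resting state functional connectivity, as compared to sham". The synopsis (1.1) puts the same idea without a sign: improvement is "correlated with degree of change in RS FC between the sgACC and DMN".

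**Pilot evidence.** Section 2.1 reports two results from the group's aiTBS data. At group level there was a "significant reduction in mean sgACC-DMN connectivity after aiTBS with significant reductions in fc between sgACC and 3 of 4 DMN nodes". At individual level, "participants with the lowest magnitude reductions in fc between sgACC and midline DMN experienced the best clinical improvements". The text finds the second result plausible by analogy with ECT, where an early decrease predicted a later increase, and uses it to motivate a dose-response study. Further on, section 2.1 mentions "the magnitude of fc change often correlating with symptom improvement", again without a sign.

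**Formal hypothesis and test.** Sections 9.1 and 9.4.3 hypothesise that "there will be a significantly greater association between the change in depression symptoms (as measured by the MADRS-S") and the connectivity change in active than in sham, with a parallel statement for IMS-12. Section 9.4.3 computes a correlation in each arm, applies Fisher's transformation and compares the two values with a two-tailed Z-test. The null of no difference "will be rejected if the Z-test has a p-value < 0.05". No other criterion is given.

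**Planning value.** Section 9.2 cites a "significant correlation between change in FC between sgACC and DMN in participants receiving open-lab aiTBS, Pearson $r = 0.51" and derives 25 participants per group from it.

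**The concern.** Section 9.4.3 tests association between individuals within each arm. That is the level at which the midline-DMN pilot result runs against section 3. A direction is stated in section 3 but is not carried into the hypotheses or the decision rule, so the rule cannot tell the section 3 pattern from the section 2.1 pattern.

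If the trial repeated the individual-level pilot pattern and reached significance, the formal hypothesis of a greater association in active could be reported as met, while the data showed that smaller reductions in connectivity go with more benefit. How to read such a result would be settled after unblinding. The sponsor's own data make that outcome realistic, and it bears directly on the mechanistic conclusion.

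**Working it through.** **1. Signs implied by the text.** Score both changes post minus pre. Higher MADRS-S means worse depression (section 8.2), so improvement is negative; a fall in connectivity is also negative.

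| Source | Pattern | Sign of r (FC change, MADRS-S change) |
|---|---|---|
| Section 3 | larger decrease, more improvement | positive |
| Section 2.1, midline DMN | smallest decrease, most improvement | negative |
| Section 9.2 | r = 0.51, scoring and second variable not given | cannot be determined |

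The printed positive sign in 9.2 does not settle the matter: if symptom change was scored as improvement instead of post minus pre, the sign flips. For IMS-12 the protocol does not say which end of the scale is better, so its predicted sign cannot be derived.

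**2. The plan's own figure.** Point-biserial model, r = 0.51, two-sided alpha 0.05 (assumed from section 9.4.1), N = 25:
- noncentrality = √25 × 0.51 / √(1 - 0.51²) = 2.55 / 0.860 = 2.96, with 23 df
- power = 0.810, and 25 is the smallest N reaching 0.80

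The stated 25 reproduces, as the number needed to test one correlation against zero. It does not depend on the sign of r.

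**3. The planned comparison.** Z = [atanh(r_active) - atanh(r_sham)] / √(2/(n - 3)).

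Inputs: |r_active| = 0.51 (section 9.2); n = 40 per arm (the primary-endpoint requirement in 9.2); r_sham = 0 (an assumption, not in the documents).
- atanh(0.51) = 0.563; √(2/37) = 0.2325
- observed active r = +0.51: Z = +2.42, p = 0.016
- observed active r = -0.51: Z = -2.42, p = 0.016

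With about 25% attrition, 50 × 0.75 = 37.5 per arm. At 37 per arm, Z = ±2.32 and p = 0.020 for either sign.

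**4. How often the rule rejects.** If the true active correlation is +0.51 or -0.51 and sham is 0, the rejection probability is Φ(2.42 - 1.96) = 67.7% at 40 per arm, the same for both signs. It is 65.3% at 38 and 77.9% at 50. The sham value matters: at 40 per arm with active +0.51, power is 34.1% if sham is +0.2 and 90.9% if sham is -0.2.

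**5. Effect of a direction condition (40 per arm, sham 0).**
- True active r as predicted: 67.7% still reject in the predicted tail. Also requiring the active-arm correlation to have the predicted sign costs at most Φ(-0.563 × √37) = Φ(-3.42), about 0.03 percentage points.
- True active r opposite: the chance of claiming support falls from 67.7% to Φ(-2.42 - 1.96) = Φ(-4.38), below 0.001%.

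**The case against.** Several points on the other side stand.

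- **The plan does not claim confirmation.** A reader might infer that it counts either direction as proof of the mechanism. Section 9.4.3 only rejects a null of no difference. Because section 3 states a direction, an attentive reader would see that an opposite-sign result contradicts it. The gap is a missing rule of interpretation.
- **Two-tailed testing is not an error.** It is standard, and sensible when theory and pilot data point different ways.
- **The pilot was not contrary as a whole.** A reader might infer that it contradicted the hypothesis outright. The group mean fell, which agrees with the primary hypothesis; the contrary pattern is individual-level and limited to midline DMN. Which nodes and which pattern lie behind r = 0.51 cannot be seen from the protocol.
- **Section 3 can be read at arm level:** active both improves mood and lowers connectivity relative to sham. On that reading, though, the within-arm correlations of 9.4.3 do not test it, and the two sections still need reconciling.
- **The tension is disclosed.** Section 2.1 presents it as a reason for the trial. It does not square it with the linear prediction in section 3.

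None of this supplies the missing sign in 9.1 and 9.4.3 or the missing scoring convention in 9.2.

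**Conclusion.** The concern holds as a gap in pre-specification for the secondary endpoints. Section 3 states a direction, the individual-level midline-DMN pilot result points the other way, and the only stated criterion accepts either. Under the assumptions of 40 evaluable per arm and sham r = 0, correlations of +0.51 and -0.51 are treated identically: p = 0.016 if observed, about 68% rejection if true. Attaching a negative sign to 0.51 is illustrative, since 9.2 does not link that figure to the midline-DMN pattern.

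Two stronger inferences are not supported. A repeat of the pilot pattern would not necessarily be significant: even with a true correlation of -0.51 against 0, the test misses about one time in three. Nor does the point reach the primary analysis, which rests on the group-by-time interaction for connectivity (9.4.2) and does not use the symptom correlation.

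**What to change.** - **9.1 and 9.4.3:** score FC, MADRS-S and IMS-12 changes as post minus pre, and state the predicted sign of the correlation for each scale, including which direction of IMS-12 is better.
- **9.4.3:** keep the two-tailed test. Claim support for the mechanism only if it is significant, the active-minus-sham difference is in the predicted direction, and the active-arm correlation has the predicted sign. Report a significant result in the other direction as contradicting the hypothesis.
- **9.2:** give the sign, DMN nodes and both variables of r = 0.51.
- **Section 3:** address the midline-DMN result from 2.1 and say why the linear decrease hypothesis is retained, or revise it.

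A further condition that the active correlation be larger in absolute size is not recommended. It would not secure a significantly greater association: at 40 per arm, active +0.31 against sham -0.30 gives Z = (0.3205 + 0.3095) / 0.2325 = 2.71, p = 0.007, and would pass with practically equal strengths.

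The cost is wording in four sections. No new data are needed, and under the assumptions above power in the predicted direction is essentially unchanged. The sponsor gives up only the option of presenting an opposite-direction result as support.

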4 STUDY DESIGN

4.1 OVERALL DESIGN

Hypothesis: Participants (n=50) receiving active aiTBS applied to DLPFC-sgACC will demonstrate a significant attenuation of RS FC between sgACC and DMN compared to sham (n=50) after each day of stimulation and these effects will accumulate linearly over the course of the 5 days of aiTBS.

Phase: This is a mechanistic study similar to a phase 2 trial.

Trial Design: Randomized, sham-controlled, double-blinded mechanistic study.

Methods to Minimize Bias: This study will achieve robust and unbiased results via several design features including: explicit inclusion/exclusion criteria; randomization of intervention condition; the use of a validated sham control; blinding; use of validated laboratory and interview/self-report measures and methods; explicit hypotheses and corresponding planned statistical analyses; power estimates; planned handling of retention/attrition and missing data; and, careful consideration of potential confounds. All experimental details will be reported in a fully transparent manner to support replication.

Dose Escalation: TMS stimulation dose will be individually determined according to 90% rMT plus depth correction, and then the aiTBS protocol will be administered with a consistent dose across all participants receiving active stimulation of 18,000 pulses/day and 90,000 pulses/course.

The goal of treatment in this study is to ensure the correct amount of treatment (90% of motor threshold) is received in the target location (L-DLPFC) rather than under-stimulating and under- treating participants. Depth correction accounts for the variable distances between the scalp and motor hotspot and scalp and treatment target from person to person. In other words, this is a personalized treatment intensity that takes into account individual variability. However, to ensure safety we never treat higher than 120% of the person's resting motor threshold, which is the standard TMS treatment intensity in routine clinical practice.

Study Arms: Two arms, active vs sham in 50:50 randomization

Site(s): Single Site (Department of Psychiatry & Behavioral Sciences, Stanford University)

Name of Study Intervention: Accelerated intermittent theta-burst stimulation (aiTBS).

Interim Analysis: N/A

Stratification: We will attempt to assess the role of gender in our analyses to determine the potential utility of additional follow-up projects that focus on any discovered gender-based observations. However, it may not be feasible to run sub-group analyses in this study because of potentially insufficient sub-group sample sizes.

Sub-Studies:

None

